**NOTES:**

- Additional parameters may be included, as required.

$AUC(0-\infty)$  will be reported if <20% of this area comes from extrapolation. However, if >40% of the AUC has been extrapolated,  $AUC(0-\infty)$  data may not be reported.

### 9.2.2. Summary Measures

All derived PK parameters will be listed. The listing will include treatment group, site ID, unique subject ID, subject ID, age, sex, race detail, analysis visit, actual dose (mg) and the PK parameters listed in [Table 3](#).

All derived PK parameters will be summarised descriptively by treatment. For each of these parameters, except Tmax, the following summary statistics will be calculated for each dose

level: median, minimum, maximum, arithmetic mean, 95% CI for the arithmetic mean, StD, between subject coefficient of variation ( $\%CV_b = 100 * (\sqrt{\exp(SD^2)} - 1)$ ) (where  $SD = SD$  of natural log transformed data), geometric mean (the  $n^{\text{th}}$  root of the product of the  $n$  values), 95% CI for the geometric mean and standard deviation of the log- transformed data. For  $T_{\text{max}}$ , median, maximum, minimum, arithmetic mean, 95% CI, and standard deviation will be calculated.

All PK parameters will be reported to at least 3 significant digits, but to no more significant digits than the precision of the original data.

The following pharmacokinetic statistical analyses will only be performed if sufficient data are available (i.e., if participants have well defined serum profiles). A minimum of 3 doses will be required to assess dose proportionality (across all treatment cohorts). Analyses may not be performed on  $C_{\text{max}}$  or  $AUC$  if the team considers there are a large amount of data either below the limit of quantification or non-calculable for at least one of the three doses.

Dose proportionality of GSK3745417 will be assessed by visual inspection of:

[figure not shown]
- Scatter plots (+geometric mean and 95% CI, as appropriate) of GSK3745417 dose-normalized PK parameter vs dose for  $AUC(0-\infty)$  [or if not calculable for the majority of participants, then  $AUC(0-t)$ ] and  $C_{\text{max}}$

The PK parameters will be dose-normalized by the actual dose that each participant received (i.e.  $C_{\text{max}}/\text{actual dose}$ ).

Analysis procedures will follow *Non-Compartmental Analysis of Clinical Pharmacokinetic Data* (VQD-REF-015788 [1.0]) and GSK PK Display Standards unless otherwise noted.

[figure not shown]

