## CONFIDENTIAL

Pharmacokinetic: Tables					
				for which LLQ was used for a particular sample.	
4.2	Pharmacokinetic	PK06	Summary of Derived GSK3745417 Plasma PK Parameters (non-transformed and log-transformed)	
Include crossover cohorts.
 
Parameters are provided in Table 3.
 
Include the footnotes:
 
Note: Participants are grouped by actual dose received at each respective visit and their originally assigned regimen schedule (Q1W or Q3W).
 
(Only add if little n is greater than N at least once)
 
Note: n (# of participants with a non-missing value used in analysis) may be greater than N (# of participants in cohort) if participant received different dose from initially assigned dose at a visit.
	SAC

[figure not shown]

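### The between-subject CV formula in SAP Section 9.2.2 has the -1 outside the square root, so as printed it is not the log-normal CV and understates it for any SD above zero

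*SAP*

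**What the plan says.** SAP Section 9.2.2 lists the descriptive statistics for the derived PK parameters and gives a formula for one of them, the between-subject CV: "CV_b = 100 * (\sqrt{\exp(SD^2)} - 1"). It defines SD as the SD "of natural log transformed data", so a CV derived on the log-normal assumption is intended.

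The scope is wide: "For each of these parameters, except Tmax, the following summary statistics will be calculated for each dose" level. The same list also asks for the "95% CI for the geometric mean and standard deviation of the log- transformed data", and for the arithmetic mean and its standard deviation. The output is Table 4.2 in SAP Section 12.10.6, "Summary of Derived GSK3745417 Plasma PK Parameters (non-transformed and log-transformed"), a deliverable for the clinical study report.

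Section 9.2.2 ends by referring to a non-compartmental analysis guidance and to "GSK PK Display Standards unless otherwise noted". Section 12.5.3 refers PK parameter summaries to the sponsor's display standards without printing a formula. No other section of the SAP gives a formula for the CV.

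**The concern.** For log-normal data the squared CV is exp(SD^2) - 1, so the subtraction has to be made before the root is taken. With the -1 outside, the printed expression reduces to exp(SD^2/2) - 1. That is the proportion by which the arithmetic mean exceeds the geometric mean, which is a different quantity from a coefficient of variation.

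At stake is one column of descriptive results for every derived parameter except Tmax, at each dose level. These include AUC(0-tau), Cmax and terminal half-life, which SAP Section 2.2 names in the secondary endpoint. Anyone quoting the CV column would quote a value that is too low, and it would not agree with the log-scale SD in the same table.

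**Working it through.** **Inputs.** The formula, the log scale of SD and the list of parameters come from SAP Section 9.2.2. The SAP states no CV or log-scale SD for any PK parameter, so there is no figure of its own to reproduce. The true CVs and SDs below are assumptions.

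**Formulas.** Let s be the SD of the natural-log values.

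- Printed: P = 100*(sqrt(exp(s^2)) - 1) = 100*(exp(s^2/2) - 1)
- Log-normal CV: C = 100*sqrt(exp(s^2) - 1)

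**Direction.** Put y = sqrt(exp(s^2)), which exceeds 1 when s > 0. Then C/100 = sqrt(y^2 - 1) = sqrt((y - 1)(y + 1)), and P/100 = y - 1. Since y + 1 > y - 1, C is larger than P for every s > 0. The understatement therefore does not depend on the amount of variability; only its size does.

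**Size by true CV.** If the true CV is c (as a fraction), exp(s^2) = 1 + c^2, so the printed formula returns sqrt(1 + c^2) - 1.

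| Assumed true CV | sqrt(1 + c^2) | Printed %CVb | True / printed |
|---|---|---|---|
| 20% | sqrt(1.04) = 1.0198 | 2.0% | 10.1 |
| 30% | sqrt(1.09) = 1.0440 | 4.4% | 6.8 |
| 50% | sqrt(1.25) = 1.1180 | 11.8% | 4.2 |
| 75% | sqrt(1.5625) = 1.25 | 25.0% | 3.0 |
| 100% | sqrt(2) = 1.4142 | 41.4% | 2.4 |
| 150% | sqrt(3.25) = 1.8028 | 80.3% | 1.9 |

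**Check by simulation.** SD divided by mean in 4 million simulated log-normal values gave 30.7% at s = 0.3 and 53.3% at s = 0.5. Formula C gives 30.7% and 53.3%; formula P gives 4.6% and 13.3%.

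**Recovery from the table.** Because the log-scale SD is also reported, a reader can insert it in C. With s = 0.5, exp(0.25) - 1 = 0.2840, and its square root is 0.533, that is 53.3%, against 13.3% in the CV column.

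**The case against.** The strongest objection is that the sponsor may not have written this formula. The point turns on where one root sign ends, and the text was read from PDF by a program. Another root in the same document is visibly damaged: the Fridericia correction in SAP Section 12.6.3 comes out as a product of two square roots where a cube root must be meant. Balanced brackets in the CV formula prove little, because a converter produces them whatever the page shows. This stands as a reason to look at the original page and to hold back from full confidence. It does not clear the text at hand, which has the -1 outside the root and is not corrected elsewhere.

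A second objection is that Table 4.2 uses a standard shell (PK06) and the SAP points to the sponsor's PK standards, so the program may already be right. That is possible, and a reader who infers that the reported CVs will certainly be wrong goes further than the document allows. But the standards apply only where nothing else is noted, and an explicit formula in the same section is such a note. A correct program would depart from the approved plan; a program that follows the plan would be wrong.

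Two stronger readings are tempting:

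- A reader might infer that the CVs would be 3 to 10 times too low in practice. That range corresponds to true CVs of about 75% down to 20%, which the SAP never states; at 100% the factor is 2.4 and at 150% it is 1.9.
- A reader might infer that the secondary endpoint or dose decisions are compromised. The endpoint in Section 2.2 is the concentrations and PK parameters themselves. Dose escalation in Parts 1A and 2A is guided by posterior DLT probabilities (Section 3.1.1), and dose proportionality is judged visually from plots with geometric means and intervals. None of these uses %CVb.

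**Conclusion.** As the text stands, the formula is wrong, and the direction of the error is certain: it understates the log-normal CV whenever SD is above zero. If programmed as written, %CVb in Table 4.2 would be too low for every derived PK parameter except Tmax, for which no CV is planned. On assumed true CVs of 20%, 50%, 75% and 100%, the printed values would be about 10, 4.2, 3 and 2.4 times too low.

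The harm is limited. This is a descriptive statistic that drives no decision in the visible plan, and the reported log-scale SD allows it to be corrected. It should be fixed, but it does not put the analysis at risk. Confidence is moderate to high; the reservation is that the extent of the root could be a reading artefact.

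**What to change.** 1. Check on the original page of Section 9.2.2 how far the root extends. If the -1 is already under it, no change to the plan is needed.
2. Otherwise state: %CVb = 100*sqrt(exp(SD^2) - 1), where SD is the standard deviation of the ln-transformed values.
3. In either case, verify the Table 4.2 program before database freeze by recomputing %CVb for one cohort from its reported log-scale SD.

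The cost is one line of text and one program check. No data, sample size or other analysis changes.

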## 1. INTRODUCTION

The purpose of this reporting and analysis plan (RAP) is to describe the analyses to be included in the Clinical Study Report (CSR) for Protocol:

Protocol Revision Chronology:		
2017N347464_00	12-SEP-2018	Original Protocol
2017N347464_01	12-DEC-2018	Protocol Amendment 1
2017N347464_02	27-AUG-2020	Protocol Amendment 2
2017N347464_03	16-OCT-2020	Protocol Amendment 3
TMF-11921930	21-APR-2021	Protocol Amendment 4
TMF-14427782	19-JAN-2022	Protocol Amendment 6
TMF-16209529	04-AUG-2023	Protocol Amendment 7

CCI

[REDACTED]

[REDACTED]

[REDACTED]. A synoptic CSR will be used to report the study and the RAP reflects the reduced list of outputs required for a synoptic CSR (and disclosure).

The RAP focuses on the outputs required for the final analysis, which will be included in the CSR. The RAP also covers two other types of reporting efforts: Dose Escalation Meetings (DEMs) and Investigator Brochure (IB) updates. Note that Statistics and Programming (S&P) provided the outputs for the monotherapy DEMs (Part 1A) and the Study Team provided outputs for the combination DEMs (Part 2A) using appropriate in-stream software. Outputs for the DEM and IB update reporting efforts, which are not required for the final analysis, are included in the RAP but are distinguished from those needed for the final analysis.

This study will utilize the system RAPIDO DV for the final analysis to aid with data visualization. Therefore, only listings that will be produced statically will be discussed in the RAP and included in the list of data displays in the Appendix. Where listings were produced statically for DEMs and IB updates, these will continue to be included in the RAP and will be distinguished as such.

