### 2.2. Study Objective(s) and Endpoint(s)

Dose Escalation (Part 1A GSK3745417 Monotherapy and Part 2A Combination GSK3745417 and Dostarlimab)	
Objectives	Endpoints
Primary Objectives	Primary Endpoints

 
To determine the safety, tolerability, and the recommended phase 2 dose (RP2D) of GSK3745417 alone or in combination with dostarlimab administered intravenously to participants with advanced/recurrent solid tumors.
 
	
 
Incidence of DLT.
 
Incidence and severity of adverse events.
 

Secondary Objectives	Secondary Endpoints

 
To characterize the PK properties of GSK3745417 alone or in combination with dostarlimab.
 
	
 
GSK3745417 concentrations in plasma and PK parameters including AUC(0-tau), maximum observed concentration (Cmax), and terminal half-life (t1/2), as data permit.
 

Exploratory Objectives	Exploratory Endpoints

CCI

[figure not shown]

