## CONFIDENTIAL

Pharmacokinetic: Figures				
				
The display will be split onto three figures, with the following cohorts included on each figure:
 
CCI
 
4.8	Pharmacokinetic	PK29	
Plot of Individual (+Geometric Mean and 95% CIs) Plasma Dose-Normalized AUC(0-inf) versus Dose
	
If AUC(0-inf) is not calculable for the majority of participants, then use AUC(0-t).
 
The mean will be provided for each treatment group and the individual participant data will be plotted, for example, with a coded symbol. The 95% CIs will be provided for the treatment groups with at least three participants.
 
Only selected visits may be included (this may mean crossover cohorts are not included as they are treated as separate visits).
 
Add the footnote: Note: Participants are grouped by actual dose received at each respective visit and their originally assigned regimen schedule (Q1W or Q3W).

4.9	Pharmacokinetic	PK29	
Plot of Individual (+Geometric Mean and 95% CIs) Plasma Dose-Normalized Cmax versus Dose
	
Use notes for the other PK29 figure including the additional footnote.

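### Dose proportionality is judged only by eye from per-group plots; a supportive power-model slope with a 90% CI would add the missing across-dose estimate at little cost

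*SAP*

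**What the plan says.** Section 9.2.2 opens the topic with "The following pharmacokinetic statistical analyses will only be performed if sufficient data are available", and adds that "A minimum of 3 doses will be required to assess dose proportionality", counted over all treatment cohorts. The team may drop Cmax or AUC if too much is below the quantification limit or cannot be calculated.

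The only visible method then follows: "Dose proportionality of GSK3745417 will be assessed by visual inspection of" one kind of display, namely "Scatter plots (+geometric mean and 95% CI, as appropriate) of GSK3745417 dose-normalized PK parameter vs dose for" AUC(0-inf) and Cmax. AUC(0-t) replaces AUC(0-inf) if the latter cannot be calculated for most participants. Normalisation uses the dose actually received.

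Section 12.10.7 lists the plots as Figures 4.8 and 4.9, with individual points and group means. It states that "The 95% CIs will be provided for the treatment groups with at least three participants" and allows the plots to be limited to selected visits. Table 4.2 also summarises every derived parameter, most of them with a geometric mean, 95% CI, coefficient of variation and log-scale SD.

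The secondary objective served is "To characterize the PK properties of GSK3745417 alone or in combination with dostarlimab" (Section 2.2). Dose proportionality is not named in the visible objectives or endpoints.

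**The concern.** Proportionality is a statement about the slope of exposure on dose over the whole range studied. The plan gives an interval for each group separately and leaves the step from those groups to a conclusion to the reader's eye. Whether the data suffice, which visits are plotted, and what the plot shows are all matters of judgement. Two readers of the same figure could write different sentences in the study report, and nothing in the plan would settle which is better supported.

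A log-log regression on the same parameters pools all doses and states how precisely the slope is known. Read against a range fixed in advance, it separates proportional, not proportional and undetermined. What is at stake is the quality of one descriptive PK conclusion. The visible escalation rules in Section 3.1.1 use DLT probabilities and do not depend on it.

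**Working it through.** The plan states no slope, sample size or acceptance range for proportionality, so there is no figure of its own to reproduce. The calculation below only illustrates what a slope estimate could deliver.

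**Inputs from the SAP**
- Starting dose 0.1 mg and 3 participants assigned at a time (Section 3.1).
- Maximum dose step two-fold; at least 9 participants at the target dose before an MTD is declared (Section 3.1.1).
- Minimum of 3 doses (Section 9.2.2).

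**Assumptions** (the dose list is redacted and PK variability is not given)
- Equal two-fold steps, with 1.5-fold as the alternative.
- Between-subject CV of 40-50%, so the log-scale SD is s = sqrt(ln(1 + CV²)) = 0.385 to 0.472.
- Equal group sizes and one profile per participant.

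**Step 1: precision the plots would show.** A group's geometric-mean 95% CI runs from the mean divided by F to the mean multiplied by F, where F = exp(t(0.975, n−1) × s / sqrt(n)).
- n = 3: exp(4.303 × 0.385 / 1.732) = 2.60, and 3.23 at CV 50%.
- n = 6: 1.50 to 1.64.
- n = 9: 1.34 to 1.44.

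**Step 2: precision of a power-model slope.** For ln(parameter) = a + b × ln(dose), with k doses of n participants and step ratio r:
- Sxx = n × (ln r)² × k(k² − 1)/12
- 90% half-width = t(0.95, N−2) × s / sqrt(Sxx), with N = k × n

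| Design | Step | Sxx | t | Half-width, CV 40% | Half-width, CV 50% |
|---|---|---|---|---|---|
| 6 doses × 3 | 2-fold | 25.22 | 1.746 | 0.134 | 0.164 |
| 4 doses × 4 | 2-fold | 9.61 | 1.761 | 0.219 | 0.268 |
| 3 doses × 3 | 2-fold | 2.88 | 1.895 | 0.430 | 0.527 |
| 6 doses × 3 | 1.5-fold | 8.63 | 1.746 | 0.229 | 0.281 |

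These are for the two-parameter model. A treatment term costs a degree of freedom, and some dose spread if the arms cover different doses, so the real intervals would be somewhat wider.

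**Step 3: reading the numbers.** A true slope of 1.2 over the 32-fold range of six doubling doses means that dose-normalised exposure rises by 32^0.2 = 2.0. That is less than F for any single group of 3 (2.60-3.23). The regression has an expected t of 0.2 × sqrt(25.22) / s, about 2.6 at CV 40% and 2.1 at CV 50%, so the same data carry usable information on the slope.

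At 3 doses × 3, an estimate of exactly 1 would still be compatible with dose-normalised exposure changing, over the 4-fold range, by a factor of 4^0.43 = 1.8 to 4^0.53 = 2.1 in either direction. There the honest result is that the data cannot decide, and a slope with its interval says so in one line.

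**The case against.** The best defence is that nothing here is wrong. Text and display list agree, the objective is to characterise PK rather than to test proportionality, and the study closed early: "the RAP reflects the reduced list of outputs required for a synoptic CSR". A descriptive plot is a defensible choice in that setting. The exploratory objectives and the hypotheses section are redacted, so a need for formal inference cannot be shown. All of this stands, and it sets the weight of the point.

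Three stronger readings are tempting, and the SAP does not support them.
- A reader might infer that the PK conclusion has no estimate and no precision at all. Section 9.2.2, Table 4.2 and Figures 4.8 and 4.9 give geometric means with 95% CIs by group. Only the across-dose estimate is absent.
- A reader might infer from the group intervals that moderate non-proportionality could not be seen. That takes one group's interval and applies it to a trend across all groups. With an expected t of 2.1 to 2.6 in the illustration, a trend may well be visible; its uncertainty is what goes unquantified. Groups may also exceed 3, and at n = 9 the interval factor falls to 1.34-1.44.
- A reader might infer that the plot hides a shortage of data. Nine points with wide intervals show imprecision plainly. What the plot lacks is a stated result.

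It is also fair to object that a bare slope adds risk. Pooling monotherapy and combination without a treatment term, or entering the same participant twice after crossover, would distort the fit. Section 9.1.1 reports assays with limits of 0.005, 5 and 0.1 ng/mL, and under the AUC(0-t) fallback, truncated profiles at low doses could make exposure look more than proportional. The slope's interval would not reflect that bias. The plots share the distortion, so this argues for specifying the model carefully, not for relying on inspection alone.

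**Conclusion.** The point holds as a modest improvement. Section 9.2.2 plans no across-dose estimate of proportionality and no precision for one, although it introduces the assessment as statistical analysis. It is not an error, and no passage contradicts another.

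The gain depends on the number and spread of doses. Under the assumptions above, the slope's 90% half-width is about 0.13-0.16 with 6 two-fold doses × 3, which is useful. It is 0.23-0.28 if the steps are 1.5-fold, and 0.43-0.53 at the 3-dose minimum with 3 per dose, where the slope would mainly document that the question is open. The actual doses, group sizes and variability may differ. A model in redacted text cannot be excluded, although the visible display list for Figures 4.8 and 4.9 gives no sign of one.

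**What to change.** Keep Figures 4.8 and 4.9 and add to Section 9.2.2 a supportive power model, log(parameter) = a + b × log(actual dose), for Cmax and AUC at Week 1. Specify:
- **Data:** one first-dose profile per participant, with crossover-period profiles excluded.
- **Treatment:** a term for monotherapy versus combination with dostarlimab.
- **Report:** b with its 90% CI, the number of dose levels, the dose range and N, described as estimation and not as a test.
- **Interpretation:** a range, fixed before database lock, for reading the slope as proportional, not proportional or undetermined.
- **Quantification limits:** profiles affected by non-quantifiable values excluded or flagged under a stated rule, with a sensitivity fit that leaves out samples from the 5 ng/mL assay.

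Actual dose and the parameters are already listed together in the PK parameter listing. The cost is one small regression, a few lines of text and one extra short table in a synoptic report. RAP version 4 is described as the final review before database lock, so the choice should be recorded before the data are final.

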## 10. EFFICACY ANALYSES

CCI

[figure not shown]

**CONFIDENTIAL**

CCI

CCI

## **12. APPENDICES**

### **12.1. Appendix 1: Protocol Deviation Management and Definitions for Per Protocol Population**

#### **12.1.1. Exclusions from Per Protocol Population**

There is no planned per protocol analysis for this study.

**12.2. Appendix 2: Schedule of Activities**

**12.2.1. Protocol Defined Schedule of Events**

See protocol Section 1.2 Schedule of Activities for detailed schedule of activities for each part.

## **12.3. Appendix 3: Assessment Windows**

### **12.3.1. Definitions of Assessment Windows for Analyses**

For PK data, the unscheduled timepoints will be slotted as below. For the remaining endpoints, data will be summarized by the nominal visits.

Elapsed time from dose to start of PK sample collection (ARELTM) in hours is calculated as  
= (start datetime of PK sample collection – reference dose datetime) /3600.

Elapsed time from dose to start of PK sample collection (ARELTM) in minutes is calculated as  
= (start datetime of PK sample collection – reference dose datetime) /60.

#### **Slotting algorithm if elapsed time (ARELTM) is in minutes**

- 0 < ARELTM <= 5, ARELTM = 5 min
- 13 <= ARELTM <= 17, ARELTM = 15 min
- 25 <= ARELTM <= 35, ARELTM = 30 mins
- 40 <= ARELTM <= 50, ARELTM = 45 mins

#### **Slotting algorithm if elapsed time (ARELTM) is in hours**

- 0.75 <= ARELTM <= 1.25, ARELTM = 1 hr
- 1.50 <= ARELTM <= 2.50, ARELTM = 2 hrs
- 3.5 <= ARELTM <= 4.5, ARELTM = 4 hrs
- 5 <= ARELTM <= 7, ARELTM = 6 hrs
- 7 <= ARELTM <= 9, ARELTM = 8 hrs
- 11 <= ARELTM <= 13, ARELTM = 12 hrs
- 16 <= ARELTM <= 20, ARELTM = 18 hrs
- 22 <= ARELTM <= 26, ARELTM = 24 hrs

